8 STUDY INTERVENTION

The surgical intervention under study is described in detail in ACLROCS_WI_InterventionalSurgicalTechniqueGuide.

8.1 Femoral Fixation Construct

Control Group: Doubled suture loop (Ethibond 6) at appropriate length determined intra-operatively connected to the femoral cortical fixation button (FlippTack, Karl Storz).

Intervention Group: Doubled suture loop (Ethibond 6) at appropriate length determined intra-operatively connected to the femoral cortical fixation button (FlippTack, Karl Storz). This construct is additionally connected to the device under study according to the interventional surgical technique guide.

8.2 Graft Preparation

Tendon preparation is done according to the in-house standard technique [Zeichnung SemiT-G-Transplantatvorbereitung Flipp-Endotack_Balgrist]. The following procedures apply for both groups under study. Three graft configurations are permitted for study inclusion. In the following, the specifics in graft preparation related to tendon configuration are outlined.

8.2.1 Semitendinosus Tendon-only Graft

The semitendinosus tendon is harvested intra-operatively as described in the following chapter. The harvested tendon is mounted on the tendon board (Karl Storz) and both tendon ends are sutured using baseball stitches (Fibre Wire 2). The tendon is folded around a doubled suture (Ethibond 6). The tendon is folded a second time and enlaced with the femoral fixation construct. The tibial fixation button (ENDOTACK®, Karl Storz) is inserted and the construct is mounted on the tendon board (Karl Storz). Three sutures are placed on the tibial side of the graft and three on the femoral side in order to create a self-reinforcing suture noose (Vicryl 2-0).

8.2.2 Doubled Semitendinosus – Doubled Gracilis Tendon Graft

The harvested semitendinosus tendon is combined with a doubled gracilis tendon due to insufficient tendon length. The tendon ends are sutured using baseball stitches and the tendons are enlaced with the femoral fixation construct. Final graft preparation is then performed equivalently to the technique using semitendinosus tendon only.

8.2.3 Quadrupled Semitendinosus – Doubled Gracilis Tendon Graft

The harvested semitendinosus tendon is combined with a doubled gracilis tendon due to insufficient tendon diameter. The tendon ends are sutured using baseball stitches and the semitendinosus tendon is folded once. The two tendons are then enlaced with the femoral fixation construct. Final graft preparation is then performed equivalently to the technique using semitendinosus tendon only.

8.3 Bone Tunnels

The harvested unsutured tendon-graft must measure between 8 and 8.5 mm in diameter at the end to be inserted into the femoral bone tunnel for subject inclusion (see chapter 7.1.2). Enlacing the OCS increases the graft diameter by 1 mm (Determined experimentally).

Accordingly, the overdrilled socket of the femoral bone tunnel has the following diameter depending on the subject's group assignment:

- Intervention group: 9 - 9.5 mm
- Control group: 8 – 8.5 mm

The tibial bone tunnel is drilled at a diameter of 8 ± 1 mm as applicable.

8.4 Surgical Technique

The surgical technique under study uses a semitendinosus tendon autograft (combined with gracilis tendon if applicable) harvested from the index knee or the contralateral knee according to the standard in-house technique. The pes anserinus is visualized through a three centimeter incision anteromedially at the proximal tibia. The semitendinosus tendon is harvested with a tendon stripper and length and thickness is measured. For the intraarticular procedure, standard medial and lateral parapatellar arthroscopy portals are used. After overdrilling with a 4.5 mm drill, the final femoral graft tunnel is created by a cannulated drill. Afterwards the tibial tunnel is prepared by using a drillguide (Karl Storz, Tuttlingen, Germany) targeted at the center of the tibial ACL footprint. The tendon graft is inserted first into the femoral bone tunnel through the medial portal. In the femoral tunnel the graft is secured using a flipping device on the cortical bone (Flipptack, KarlStorz, Tuttlingen, Germany). Tibial graft-fixation is achieved using an interference screw (Megafix, Karl Storz, Tuttlingen, Germany) proximally, and a small plate (Endotack, Karl Storz, Tuttlingen, Germany) covering the bone tunnel distally.

The table below shows a schematic of the surgical techniques for graft fixation under study and the material in use.

Control Intervention	Experimental Intervention

1) Femoral cortical fixation: Flipptack (Karl Storz) 2) Femoral Graft suspension: Ethibond 6 (Ethicon Inc.) Suture bone tunnel; diameter: 4.5 mm 3) Cannulated bone tunnel; diameter: 8 – 8.5 mm Length: 27 mm 4) Tendon graft 5) Resorbable interference screw fixation (Megafix, Karl Storz) 6) Tibial bone tunnel; Diameter: 8 – 8.5 mm Tibial Graft suspension: Fibre Wire 2 (Ethicon Inc.) and Ethibond 6 7) Tibial cortical fixation: Endotack (Karl Storz)
	
1) Femoral cortical fixation: Flipptack (Karl Storz) 2) Femoral Graft suspension: Ethibond 6 (Ethicon Inc.) Suture bone tunnel; diameter: 4.5 mm 3) Cannulated bone tunnel; diameter: 9 – 9.5 mm Length: 27 mm 4) Tendon graft 5) Resorbable interference screw fixation (Megafix, Karl Storz) 6) Tibial bone tunnel; Diameter: 8 – 8.5 mm Tibial Graft suspension: Fibre Wire 2 (Ethicon Inc.) and Ethibond 6 7) Tibial cortical fixation: Endotack (Karl Storz) Black Arrow: Medical device under study enlaced into tendon graft.

8.4.1 Interventional Product

Brand name	SmartBone®
Type	Block BTB-Converter
Dimensions	8x11 mm
Manufacturer	Industrie Biomediche Insubri
Description	SmartBone® is a composite xeno-hybrid Class III CE marked Medical Device, composed of bovine-bone derived porous mineral matrix, reinforced with a blend of collagen fragments (in the form of hydrolysed gelatine) and biopolymers (i.e. resorbable aliphatic block-copolymers), intended for use in bone regeneration applications in reconstructive surgeries. SmartBone® is a long-term implantable, resorbable, sterile medical device, which is supplied in different shapes and dimensions to best match surgical needs. From big (15 x 30 x 60 mm ³) solid blocks to granulates (1-2 mm and 2-4 mm) to fine microchips (0.25-1mm).
Intended use (according to IFU)	SmartBone® is recommended for reconstructing and filling bone defects and for bone augmentation. For example, SmartBone® is recommended for filling bone defects and for bone augmentation in the following cases: 
 Augmentation/reconstruction of the alveolar ridge; Alveolar filling after extraction; Implants: preparation of the implant bed, filling of the bone dehiscences, augmentation of the sinus floor; Periodontology: filling of bone defects, providing support for the membrane in guided tissue regeneration (GTR).
Intended user and patient population	SmartBone is intended for professional use only. It should be used by trained surgeons, e.g. orthopedic surgeons, neurosurgeons, plastic surgeons, oral and maxillofacial surgeons and trained dentists. The patient population consist of adults (age 18+; skeletally mature subjects) with edentulous areas or bone defects.
CE Declaration of Conformity	Yes
Device Materials	Bovine derived matrix: 
 Calcium hydroxyapatite (Ca₅(PO₄)₃(OH)) Minor collagen residuals Coating: 
 Poly(L-lactide-co-ε-caprolactone) Polysaccharides

8.4.2 Packaging, Labelling and Supply (Re-Supply)

Upon receipt of the study device supplies, an inventory must be performed and a device receipt log filled out and signed by the person accepting the shipment. It is important that the designated study staff counts and verifies that the shipment contains all the items noted in the shipment inventory. Any damaged or unusable study devices in a given shipment will be documented in the study files.

Regular study device reconciliation will be performed to document assigned and used devices. This reconciliation will be logged on the device accountability form, and signed and dated by the study team.

8.4.3 Storage Conditions

The device under study is stored in a secure, limited access area under the recommended storage conditions. It is to be stored in its original package in a dry place and away from direct sources of light or heat at temperatures between 2 and 25°C.

8.5 Modifications of Device Application

Modifications of the device under study or of its application are not planned.

8.6 Compliance with Study Intervention

No postsurgical exclusion criteria related to patient compliance are defined.

8.7 Data Collection and Follow-up for Withdrawn Participants

For subjects who withdraw from the study prior to completion, the site will attempt to contact the subject in order to obtain safety information.

8.8 Trial Specific Preventive Measures

In case of complications during ACL-reconstruction using the investigational product, the standard technique will be applied. The patient will be excluded from further analysis, the reason for exclusion will be recorded. Before every CT-scan, female patients will undergo pregnancy testing. Female patients of child bearing potential will have agreed in the informed consent form, to use contraception during the first 24 months of the study.

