Number of Participants with Rationale:	A total of 56 patients are required to detect a minimal clinically important difference in relative change of bone tunnel volume after a 2-year follow-up of 20% given an assumed standard deviation of 25.2% with a power of 0.8 and an α -error of 0.05 and accounting for a drop-out rate of 10% for this equally sized two-group parallel design.
Study Duration:	Expected duration for patient acquisition: 22 months Expected time from first patient acquisition to the end of follow-up of the last patient: 82 months Statistic and Abstract: ca. 6 months
Study Schedule:	First-Patient-In: 07/2017 Last-Patient-Out: 05/2024 Statistics/Abstract: 12/2024
Investigator(s):	PD Dr. med. [name] University Hospital Balgrist
Study Centre(s):	University Hospital Balgrist
Statistical Considerations:	Intention-To-Treat analysis Independent t-test on the primary efficacy outcome comparing the two groups with a significance level of 0.05, 2-sided.
GCP Statement:	This study will be conducted in compliance with the protocol, the current version of the Declaration of Helsinki, the ICH-GCP or ISO EN 14155 (as far as applicable) as well as all national legal and regulatory requirements.

STUDY SUMMARY IN LOCAL LANGUAGE

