5 STUDY OUTCOMES

5.1 Primary Outcome

The primary outcome variable of this study is the relative change of the CT evaluated femoral bone tunnel volume from baseline to follow-up at 12 months.

As the primary objective of the use of the OCS is to reduce tunnel widening by promoting bony ingrowth into the bone tunnel, the relative change of bone tunnel volume over time is an appropriate measure to quantitatively assess this effect. Assessing relative changes as opposed to absolute values negates the potential for bias by different tunnel drill sizes used in the two treatment arms potentially influencing the absolute ossification/de-ossification. In quantifying bone tunnel size, CT measurements provide substantially more reliable means than plain radiography or magnetic resonance imaging [50, 68].

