7.4 Criteria for Withdrawal/ Discontinuation of Participants

If during the course of the study, a participant meets an exclusion criterion, he will be withdrawn from the study. Specifically, a potential rerupture of the graft will lead to exclusion of the patient. In any case of premature discontinuation of a participant, the reason will be documented in the respective eCRF.

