9.3.2 Baseline (Visit 2)

9.3.2.1 Admission Interview

Eligible Patients giving oral consent to study participation will be interviewed by the SN for detailed screening of inclusion/exclusion criteria. A patient information eCRF will be filled covering all necessary points for temporary admission of the patient into the study. Definite admission can only be acquired after the surgery. The signed informed consent form will be validated by signature by the PI and stored in the patient's trial file. The patient will receive a copy of the signed informed consent form. For female patients of child bearing potential, a pregnancy test will be performed. The result of the pregnancy test will be photographed and the photograph will be signed by the PI and filed. The patient will be given the opportunity to clarify all uncertainties concerning the trial and the upcoming surgery with the PI. Also recorded will be the medical history and patient demographics. At this stage the preinjury activity level using Tegner activity scale will be assessed.

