9.3.2.3.2 Randomization

Patient randomization is acquired intraoperatively only if all inclusion criteria and no exclusion criteria have been met. The folded tendon-graft (not sutured, without OCS) must measure 8 – 8.5 mm in diameter at the end which is to be inserted into the femoral bone tunnel. If no intraoperatively assessed exclusion criteria are met (e.g. tendon-graft specifications, severe cartilage damage, extensive meniscus resection necessary) the subject is allocated to one of the two treatment groups. The envelope for the randomized group allocation of the subject is opened and the surgical procedure is carried out respectively. The envelope is sealed again afterwards and stored in the patient's trial file. The randomization procedure is described in detail in ACLROCS_WI_Randomization.

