11.4.1 Datasets to be analyzed, analysis populations

Statistical analysis is based on the intention-to-treat analysis. In the case of the current trial this means that patients not following the rehabilitation protocol will not be excluded from analysis.

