11.5 Handling of Missing Data

Missing data will be left missing, i.e. no imputation scheme will be used. All data from a subject will be used for analysis, irrespective of possibly missing values.

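### Section 8.8 drops scaffold-arm patients from analysis after a device complication: a one-sided exclusion after randomisation that conflicts with the stated intention-to-treat analysis

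*Combined protocol and SAP*

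**What the plan says.** Section 8.8 deals with complications that occur during reconstruction with the investigational product. The operation is completed with the standard technique, and then "The patient will be excluded from further analysis, the reason for exclusion will be recorded". The section does not define a complication, does not limit the exclusion to efficacy, and has no counterpart for control patients.

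The analysis population is described differently elsewhere. The synopsis, under Statistical Considerations, lists "Intention-To-Treat analysis". Section 11.4.1 states: "Statistical analysis is based on the intention-to-treat analysis". It then explains the term for this trial by one example only, patients who do not adhere to rehabilitation. Section 11.5 adds: "All data from a subject will be used for analysis, irrespective of possibly missing values".

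On timing, 9.3.2.3.2 (Randomization) says: "Patient randomization is acquired intraoperatively only if all inclusion criteria and no exclusion criteria have been met". The envelope is then opened and the allocated procedure carried out. Section 9.3.2.1 says of enrolment: "Definite admission can only be acquired after the surgery".

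A separate rule in 7.4 covers graft failure: "Specifically, a potential rerupture of the graft will lead to exclusion of the patient". It applies to both arms and does not mention analysis.

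**The concern.** A patient can have a complication with the scaffold only after being allocated to it. Complications during surgery can happen in either arm, but the exclusion can apply in only one. The control arm keeps every patient, including any with a difficult operation, while the intervention arm loses its difficult cases. Randomisation no longer protects that comparison.

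The excluded patients may plausibly differ on the primary outcome. Section 3.6 lists soft tissue bridging and scaffold breakage as risks during graft insertion. Section 8.4 describes drilling the femoral tunnel before the graft goes in, and 8.3 gives a socket of 9 to 9.5 mm for the intervention arm against 8 to 8.5 mm for controls. A patient converted at insertion could therefore have a graft without a scaffold in a socket drilled for one. Section 3.1.1 names graft motion in the tunnel as a mechanical cause of widening. This is an inference from the protocol's text, not a documented result.

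The decision to convert is made by an operator who knows the allocation (6.3.2). The exclusion would also reach the interim inferiority rule in 11.3 and 11.4.5. With 10 patients per arm there, a single exclusion is 10% of the arm. Read literally, it would also take these patients out of the safety tabulations in 11.4.6, although 5.4 makes intra-operative complications a safety outcome.

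**Working it through.** **Order of events**

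1. Eligibility is confirmed during surgery (9.3.2.3.2).
2. The envelope is opened and the patient is randomised (7.3, 9.3.2.3.2).
3. The allocated procedure is carried out. The scaffold is used in the intervention arm only (8.1).
4. If a complication occurs with the scaffold, the patient is converted and excluded from analysis (8.8).

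Step 4 follows step 2 and can happen in one arm only. The remark in 9.3.2.1 about definite admission after surgery does not undo step 2.

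**The plan's own sample size (11.2)**

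Inputs: difference 20 percentage points (pp), SD 25.175 pp, two-sided alpha 0.05, power 0.80, drop-out 10%.

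- Normal approximation: n = 2 × (1.960 + 0.842)² × (25.175/20)² = 24.9, so 25 per group.
- Drop-out: 25/0.9 = 27.8, so 28 per group and 56 in total.

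Both stated figures reproduce. The exact t-test needs 26 per group; its power at 25 is 0.786.

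**Loss of power from the exclusion**

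Starting from 28 per arm, exact t-test power is 0.831 with no exclusion. It is 0.824, 0.817 and 0.809 with 1, 2 and 3 intervention-only exclusions. Power is not the problem.

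**Possible bias**

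Assumptions, none of them in the documents:
- k = 1, 2 or 3 of 28 scaffold patients are excluded (3.6% to 10.7%).
- Their relative volume change would have been d SD worse than that of the rest of their arm.
- There is no true treatment effect, so the control arm contains k comparable patients, who stay in.

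Shift of the intervention mean = (k/28) × d × 25.175 pp. Example: k = 3, d = 2 gives (3/28) × 2 × 25.175 = 5.39 pp, which is 5.39/20 = 27% of the target difference.

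The chance of a significant result favouring the scaffold (nominal 2.5%) comes from simulating 100,000 trials per cell: 28 controls against 28 − k scaffold patients, Student's t-test, two-sided 0.05.

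| d (SD) | k | Shift towards scaffold (pp) | False result favouring scaffold |
|---|---|---|---|
| 0 | 1, 2, 3 | 0 | 2.5% |
| 1 worse | 1 | 0.90 | 3.2% |
| 1 worse | 2 | 1.80 | 4.1% |
| 1 worse | 3 | 2.70 | 5.1% |
| 2 worse | 1 | 1.80 | 3.7% |
| 2 worse | 2 | 3.60 | 5.6% |
| 2 worse | 3 | 5.39 | 8.2% |
| 1 better | 1, 2, 3 | −0.90, −1.80, −2.70 | 1.7%, 1.2%, 0.9% |

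Repeat simulations agree to within about 0.2 percentage points. Total two-sided error is 0.049 to 0.084 over the cells from 0 to 2 SD worse.

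**The case against.** The case for leaving 8.8 alone, or treating it as minor, has several parts.

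- **No literal contradiction.** Section 11.4.1 gives intention-to-treat a trial-specific meaning, limited to rehabilitation, and 8.8 does not conflict with that sentence. This is true as far as it goes. The conflict is with the ordinary meaning of the term used in the synopsis and 11.4.1. The example in 11.4.1 does not authorise another exclusion.
- **Events may be rare or absent.** Section 3.6 reports no scaffold damage in vitro at 250 N, no soft tissue bridging in cadaver tests, and bridging as correctable during surgery. The count may well be zero, and then the rule has no effect. This stands, and it is why the figures above are illustrations only.
- **The sign is not established.** Excluded patients could do better, and the bias would then run against the scaffold. This also stands. It is no defence of the rule, because the comparison is distorted either way.
- **The data may still exist.** Section 8.8 excludes patients from analysis without saying that their visits stop, so a sensitivity analysis might be possible. That is fair. However, the plan neither secures the follow-up nor specifies such an analysis.
- **Converted patients may have a mismatched graft and socket.** Section 5.1 argues "Assessing relative changes as opposed to absolute values negates the potential for bias by different tunnel drill sizes", but it has the planned difference between arms in mind, not a conversion after drilling. It gives only limited support for including these patients. The case for keeping them rests on randomisation; a mismatch that follows from attempting the scaffold is part of what that strategy delivers.
- **Re-rupture is a different matter.** It affects both arms, and 11.5 already keeps collected data. Agreed: it is a secondary point of wording.

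**Conclusion.** The concern holds. Section 8.8 prescribes an exclusion after randomisation that only the intervention arm can trigger, and it is incompatible with the intention-to-treat analysis the plan names. That conclusion comes from the text and depends on no assumed number.

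The size of the resulting bias cannot be determined from the documents. Under the stated assumptions (1 to 3 exclusions among 28, outcomes 0 to 2 SD worse) it ranges from nothing to 5.4 pp, with a false-positive chance in the scaffold's favour of 2.5% to 8.2%. The upper end needs three exclusions, all 2 SD worse. The rule should nevertheless be corrected, because it decides who enters the primary comparison and any follow-up not collected cannot be recovered.

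**What to change.** - **Analysis set.** In 8.8 and 11.4.1, define the primary analysis set as all randomised patients in the group to which they were allocated. Apply the same definition to the interim analysis and the safety tabulations.
- **Follow-up.** State that patients changed to the standard technique stay in CT, questionnaire and stability follow-up. Their own post-operative CT serves as baseline.
- **Sensitivity analysis.** Use the 8.8 exclusion only in a labelled per-protocol sensitivity analysis. Define beforehand what counts as a complication, and report the number and reasons.
- **Re-rupture.** Reconcile 7.4 with 11.4.1 and 11.5 by stating that data collected up to the re-rupture remain in the analysis. Report re-ruptures by arm beside the stability results. A 12-month CT missed because of an earlier re-rupture stays missing, since no imputation is planned.

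The cost is protocol wording and, if these visits were not already intended, follow-up for the few converted patients. The total stays at 56. The estimate may be somewhat less favourable to the scaffold. No change to the surgical fallback is proposed.

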8.9 Concomitant Intervention(s)

Allowed concomitant surgical interventions are defined in the inclusion/exclusion criteria and will be recorded in the eCRF. No specific postsurgical concomitant rehabilitation therapies are prohibited. The patient will be advised to inform the treating physician about the participation in the clinical trial in the case he receives treatment - related or unrelated to the intervention under study – outside of the study protocol.

